8.2.2. TRIM-Diabetes Questionnaire

The TRIM-Diabetes questionnaire is a 28-item treatment satisfaction measure with 5 domains assessing treatment burden, daily life, diabetes management, compliance, and psychological health. Measures can be scored independently for each domain or as a total score. Higher scores indicate a better health state.

The TRIM-Diabetes will be administered in this study at baseline, Week 10, and Week 26 to assess treatment satisfaction within each treatment group of the study.

There are three steps for the calculation of TRIM- Diabetes scores. The first step is to reverse the coded value for questions in daily life, compliance, and psychological health domains, so that a higher score indicates better health for all domains. In the second step, raw scale scores are computed by summing across items in the same domain (raw domain scores). A total raw score can also be calculated. In last step, raw scale scores are transformed to a 0-100 scale (transformed scale scores) using the following: Domain= $[(\text{raw score} - \text{lowest possible raw score}) / \text{possible raw score range}] \times 100$.

Change from baseline in TRIM-Diabetes total score and individual domain scores will be summarized descriptively by visit and treatment group, and analyzed using a similar MMRM model as Model 2 where TRIM-Diabetes scores replace weight.

Every effort will be made to minimize the amount of missing data and therefore maximize the quality of the data collected. If a patient answers at least half of the items in a multi-item domain (or half plus one in the case of domains with an odd number of items) then a domain score should be calculated. The average score (across completed items in the same domain) for that patient will be used to estimate any missing item in that domain. For example, if a patient leaves a blank item in the 5-item Diabetes Management domain, substitute the patient's average score (across the four answered Diabetes Management items) for the score for that item.

If more than one answer is ticked off by the patient (adjacent answers or not) the item should be coded as missing.

8.2.3. HFS-II Worry Subscale

The HFS-II questionnaire is a 33-item questionnaire with 2 subscales that measure: 1) behavior to avoid hypoglycemia and its negative consequences and 2) worries about hypoglycemia and its negative consequences. This study will include the worry subscale only (18 items, score range 0 to 72). Responses use a 5-point Likert scale ranging from Never to Always. The HFS-II has a 6-month recall period.

The HFS-II will be administered in this study at baseline, Week 10, and Week 26 to assess within each treatment group worries about hypoglycemia.

The continuous endpoint of HFS-II worry subscale score change from Baseline by visit will be analyzed using an MMRM model similar to Model 2 where HFS-II worry subscale score replaces weight.

If a subject missed one or more items, or ticked multiple items, the data will be handled in the same as for TRIM-Diabetes questionnaire items.

8.2.4. HbA_{1c} Change from Baseline at Week 26 by Baseline FPG Tertiles

The minimum, 33% percentile, 66% percentile and the maximum values of baseline FPG concentration will be obtained from the valid FPG values at baseline. The subjects will be stratified into 3 groups with their baseline FPG concentration <33% percentile (1st FPG Tertile), ≤33% to <67% percentile (2nd FPG Tertile), and the rest (3rd FPG Tertile). HbA_{1c} values will be summarized descriptively by baseline FPG tertiles, by visit and treatment. The MMRM model for the subgroup analysis on the primary efficacy endpoint (Section 7.1.1.3) will be used in the FA population for this analysis.

8.2.5. FPG Change from Baseline at Week 26 by Baseline FPG Tertiles

This endpoint will be summarized descriptively and analyzed using a similar model as used for the analysis in Section 8.2.4, with FPG change from baseline as the response variable and adding baseline FPG tertile as covariate (Refer to Appendix 11 for model specification and SAS code).

8.2.6. 8-Point SMBG Profile and Mean Daily Blood Glucose

An 8-point blood glucose profile will be performed by the subject 3 times in the week prior to Baseline, Week 10 and Week 26. Subjects will be instructed to measure and record glucose values from their glucose meter at the following times:

- Before breakfast (at least 8 hours without food intake)
- 2 hours after breakfast
- Before lunch
- 2 hours after lunch
- Before dinner
- 2 hours after dinner
- At bedtime
- At 2 AM

Glucose concentrations at each of the 8 time points will be averaged over three days with the largest count of 8-point SMBG data points within the visit window to derive the mean glucose concentrations at each time point. If there are ties for these counts within the visit window, select the one closest to the actual visit day. If subject only had 1 or 2 days of 8-point SMBG within the visit window, use 1 day 8-point SMBG or average of 2 days of 8-point SMBG data. The daily average of glucose concentrations will be calculated as the average over the glucose concentrations at the 8 time points. The daily average data will be calculated only if at least one pair of preprandial and postprandial glucose values is available. Only complete pairs of preprandial and postprandial glucose values will be used for the calculation.

Visit window will be defined for the purpose of SMBG calculation. It will be defined by study day according to following table.

Table - Visit Window for SMBG Calculation

Visit	Target Study Day	Range of Study Day
Baseline	1	Study day <= 1
Week 10	71	43 <= study day <= 99
Week 26	183	155 <= study day <= 211

The absolute glucose concentrations and change from Baseline at each time point will be summarized descriptively by treatment and visit for the FA population. The daily average glucose concentration and change from Baseline will be summarized similarly. The absolute glucose concentrations will also be plotted by visit, time points and treatment.

Daily average glucose concentrations will be analyzed similarly to weight, with a MMRM model (Model 2) with daily average glucose replacing weight in the model (Section 8.1.2.3). The analyses will be performed on FA population and all data will be listed.

8.2.7. Number and Percentage of Subjects with ≤ 1 kg Weight Gain at Week 26

Number and percent of subjects with ≤ 1 kg weight gain at Week 26 will be analyzed in the same manner as specified in Section 8.1.2.2.

8.2.8. Percentage of Subjects Achieving $\text{HbA}_{1c} < 7.0\%$ without Weight Gain and without Hypoglycemia with Blood Glucose < 3.1 mmol/L (< 56 mg/dL) regardless of Symptoms at Week 26

This composite endpoint will be analyzed in the same manner as specified in Section 8.1.2.2.

8.2.9. Proportion of Subjects Treated with Once-Weekly Albiglutide That Are Able to Totally Decrease Prandial Insulin without Worsening HbA_{1c} Control at Week 26

Worsening HbA_{1c} is defined as $> 0.3\%$ increase in HbA_{1c} compared to baseline at Week 26. This exploratory endpoint will be analyzed in the same manner as specified in Section 8.1.2.1.

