5.7.1. Treatment Between Week 26 (End of Treatment)/Early Withdrawal and Follow-up

After completion of the end-of-treatment (Week 26) or early withdrawal visits, subjects will return to the study center in 4 weeks for the Follow-up visit. During this time, subjects will continue insulin glargine or insulin glargine plus insulin lispro to maintain adequate glycemic control.

For subjects in the albiglutide plus insulin glargine treatment arm, the last dose of once-weekly albiglutide will occur at Week 25. As needed, insulin lispro may also be re-introduced during this period according to the re-introduction of insulin lispro algorithm provided in Section 5.1.3.5. Insulin glargine alone (in subjects for whom insulin lispro has not been re-introduced) or insulin glargine and insulin lispro (in subjects for whom insulin lispro has been re-introduced) can be adjusted to achieve or maintain glycemic targets as close to normal as possible without untoward hypoglycemia

in accordance with product labeling in the respective country and standards of care at the study center.

For subjects in the insulin glargine plus insulin lispro treatment arm, both insulin glargine and insulin lispro may be adjusted to achieve or maintain glycemic targets as close to normal as possible without untoward hypoglycemia in accordance with product labeling in the respective country and standards of care at the study center.

Note: During this time, subjects must not use any prohibited medications or nondrug therapies (see Section [5.6.2](#)).

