6. STUDY ASSESSMENTS AND PROCEDURES

Study assessments and times are presented in [Table 5](#). Telephone contact and times are presented in [Table 6](#). Study center visits through Week 16, inclusive, and all telephone contacts will have a visit window of \pm 3 days; study center visits occurring after Week 16 will have a visit window of \pm 7 days. Subjects will not be considered out of compliance if visit windows extend because of extraordinary events that make it impossible for subjects to complete a visit within the visit window (e.g., holidays, vacations, personal emergencies). However, determination of the maximum visit window deviation is at the discretion of the medical monitor.

Table 5 Time and Events Table – Study Visits

Study Procedure		Screening	Standardization	Treatment (For scheduled telephone calls, see Table 6)							Early Withdrawal Visit ¹	Follow-up Visit
				Baseline/ Randomization								
	Visit	1	2	3	4	5	6	7	8	9		10
	Week ²	-6 to -5	-4 ³	-1	0 ³	4	5 ³	10 ³	18 ³	26 ^{3,4}		30
Obtain written informed consent		X										
Obtain subject demography		X										
Obtain medical history		X										
Obtain disease history		X										
Obtain therapy history		X										
Review of inclusion/exclusion criteria		X	X	X	X							
Review of randomization criteria					X							
Efficacy Assessments												
Dispense home glucose monitoring device and e-diary			X									
Collect e-diary from subject												X
Provide advice on diet, exercise, home glucose monitoring, and hypoglycemia ⁵			X	X	X	X	X	X	X	X		X
Obtain 8-point SMBG profile ⁶					X			X		X		
Review glucose monitoring with subject ⁵				X	X	X	X	X	X	X		X
Administer diabetes questionnaires ⁷					X			X		X		X
Obtain daily insulin dose information ⁸					X	X	X	X	X	X		X
Safety Assessments												
Review concomitant medication		X	X	X	X	X	X	X	X	X		X
Perform physical examination ⁹		X			X			X		X		X
Check visual acuity and funduscopy ¹⁰		X							X	X		
Obtain vital sign measurements ¹¹		X	X	X	X	X	X	X	X	X		X
Obtain body mass index information ¹¹		X										
Perform 12-lead ECG ¹²		X			X					X		X
Assess for adverse events			X	X	X	X	X	X	X	X		X
Assess for serious adverse events		X	X	X	X	X	X	X	X	X		X
Assess for hypoglycemic events ¹³		X	X	X	X	X	X	X	X	X		X

Study Procedure		Screening	Standardization	Treatment (For scheduled telephone calls, see Table 6)						Early Withdrawal Visit ¹	Follow-up Visit			
				Baseline/ Randomization										
				Visit	1	2	3	4	5	6	7	8	9	10

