NOTE: The use of a GLP-1R agonist (albiglutide) is expected to decrease the need for insulin and, therefore, the investigator will need to ensure careful follow-up of each subject accordingly.

6.2.2.2. 8-Point Self-Monitored Blood Glucose Profile

An 8-point glucose profile will be performed by the subject 3 times in the week prior to the Baseline/Randomization visit (Visit 4, Week 0), Visit 7 (Week 10), and Visit 9 (Week 26). Subjects should be instructed to measure and record blood glucose values using their glucose meter at the following times:

- Before breakfast (at least 8 hours without food intake)
- 2 hours post-breakfast
- Before lunch
- 2 hours post-lunch
- Before dinner
- 2 hours post-dinner
- At bedtime
- At 2 AM

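### SAP 8.2.6 can count self-monitored glucose readings taken after the Week 26 visit as Week 26; the effect is probably very small, and a cap at the visit date removes it

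*SAP*

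**What the plan says.** - **Schedule.** Protocol 6.2.2.2: "An 8-point glucose profile will be performed by the subject 3 times in the week prior to the Baseline/Randomization visit", and likewise before Weeks 10 and 26. SAP 8.2.6 repeats this.
- **Window.** The SAP 8.2.6 table gives Week 26 a target of Day 183 and a range of "155 <= study day <= 211".
- **Choice of days.** Readings are "averaged over three days with the largest count of 8-point SMBG data points within the visit window". Then: "If there are ties for these counts within the visit window, select the one closest to the actual visit day". A subject with only one or two 8-point days in the window uses those. A daily average needs at least one complete pre-meal and post-meal pair, and only complete pairs are used.
- **Treatment after Week 26.** Protocol 5.7.1 says the last dose of "once-weekly albiglutide will occur at Week 25. As needed, insulin lispro may also be re-introduced during this period". The control arm stays on glargine plus lispro.
- **Data source.** In Protocol Table 5 the item "Collect e-diary from subject" falls at the Follow-up visit, so readings from after Week 26 can exist.
- **General rules.** SAP 11.3.4 sets the Week 30 target at Day 211. It also says that SMBG analyses use the visits and visit dates on the eCRF.

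**The concern.** The window is much wider than the collection period and extends on both sides of the visit. Closeness to the visit only breaks ties, and it works in either direction. Readings taken after the Week 26 visit can therefore be labelled Week 26 although treatment has changed, mainly in the albiglutide arm.

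The SAP deals with this change of treatment for other outcomes. SAP 6.7 stops counting lispro re-introduction at Week 25, because lispro may be prescribed at Week 26 as ordinary care. SAP 8.1.2.4 takes the albiglutide arm's Week 26 insulin dose from the Week 25 prescription. SAP 8.2.6 has no such limit.

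At stake are the Week 26 values in the 8-point profile summary (Table 2.401) and the daily-average glucose model (Table 2.403).

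**Working it through.** **Inputs.** Day 1 is the first dose (SAP 5.4), so the target day for week *w* is 7*w* + 1. The Week 26 visit may move by ±7 days (Protocol Table 5, footnote 2). The SAP's on-therapy limit for albiglutide is last dose + 25 days (SAP 5.5). The half-life is about 5 days.

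**1. Reproduce the window.** Week 26: 7 × 26 + 1 = 183, and 183 ± 28 = Days 155 to 211. Week 30: 7 × 30 + 1 = 211. The upper bound is exactly the follow-up target.

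**2. Window against schedule.** The window has 211 − 155 + 1 = 57 days. The scheduled week before a Day 183 visit is Days 176 to 182, which is 7 days.

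**3. Window days after the visit.**
- Visit on Day 176: 211 − 176 = 35
- Visit on Day 183: 211 − 183 = 28 (49% of 57)
- Visit on Day 190: 211 − 190 = 21

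**4. Time since albiglutide.** The last dose falls on 7 × 25 + 1 = Day 176. The on-therapy limit is 176 + 25 = Day 201, so Days 202 to 211 (10 days) are post-therapy by the SAP's own rule. The share of the last dose remaining is 0.5^(7/5) = 38% at Day 183 and 0.5^(35/5) = 0.8% at Day 211.

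**5. Early withdrawals.** With withdrawal on Day *d* and follow-up at *d* + 28, follow-up reaches the window when *d* ≥ 127. For *d* = 127 to 154, every reading from Day 155 to *d* + 28 is after withdrawal, yet it falls in the Week 26 window.

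**6. Which readings can get in.** The routine readings in Protocol 6.2.2.1 are before each of the three meals and at bedtime. They contain no 2-hour post-meal value, so alone they form no pair and give no daily average. The rule for subjects with only one or two 8-point days also implies that routine days are not 8-point days. If they were, almost nobody doing four tests a day would have so few in 57 days. Two routes remain: a profile done late, and days after the visit with the extra post-meal checks that Protocol 6.2.2.1 lets the investigator request. The pair rule covers the daily average only, not the time-point means in Table 2.401.

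**7. Does SAP 11.3.4 close the gap?** No. Its sentence on eCRF visit dates supplies a date for the tie rule but sets no upper limit, and SAP 8.2.6 defines the window by study day.

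**8. Illustration on assumed inputs.** Shift in arm mean = share affected × (days after visit ÷ 3) × glucose difference. The documents give none of these inputs.
- 1% affected, one day, 1 mmol/L: 0.01 × 1/3 × 1 = 0.003 mmol/L
- 10% affected, one day, 2 mmol/L: 0.10 × 1/3 × 2 = 0.067 mmol/L
- 10% affected, all three days, 2 mmol/L: 0.10 × 3/3 × 2 = 0.20 mmol/L

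**The case against.** The case for leaving the rule alone is strong on size.

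- **Other SAP 8.2.6 rules block most routine readings.** The pair rule and the one-or-two-days rule do this, and no profile is scheduled after Week 26. This stands. A subject with three full 8-point days before the visit is affected only if a full day after it lies closer.
- **Albiglutide does not stop acting at Week 26.** The Week 26 visit itself comes about 7 days after the last dose, and Protocol 5.7.2 says therapeutic concentrations persist for 3 to 4 weeks. This stands for the drug. It does not cover a lispro restart, which can act from the visit onward.
- **The general Week 26 window also runs past the visit.** In the albiglutide arm it ends at nominal Day 201. In the control arm it ends at the last dose date, which SAP 11.4 sets to the Week 30 visit for completers. This stands: the general window is not a clean guard either, so the argument rests on the protocol schedule and the Week 25 cut-offs in SAP 6.7 and 8.1.2.4.
- **A cap at the visit is stricter than the SAP's other efficacy windows.** It would discard a profile done a few days late. True, and this is the cost of the fix.

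A reader might also infer that the Week 10 range, "43 <= study day <= 99", needs the same cap because it too extends past its visit. The documents do not support that: subjects who continue are on their randomized regimen throughout those days.

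**Conclusion.** The gap is real, and its effect is probably very small. As written, SAP 8.2.6 can label readings from after the Week 26 visit as Week 26, and no other section prevents it. The dates are certain; how many subjects would be affected is not in the documents and is probably few.

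Two stronger readings should be resisted. The first is that about half of the Week 26 glucose data is off treatment. The 28 of 57 is a count of calendar days, and most of those days should contribute nothing. The second is that the rule favours one arm. Fading albiglutide would raise glucose and restarted lispro would lower it, so the direction cannot be determined.

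The outputs are exploratory and outside the testing order in SAP 11.10. The HbA1c non-inferiority test, type I error and power do not depend on them. The day counts assume dosing and visits on target, apart from the ±7 days shown. The mmol/L figures rest wholly on assumed inputs, and 0.20 is the largest only among those.

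**What to change.** In SAP 8.2.6, restrict Week 26 SMBG to readings on or before the actual Week 26 visit date or, for early withdrawals, the early withdrawal visit date. State the same rule in SAP 11.3.4 so that the two sections agree. Keep the lower bound, the day-selection rule and the Week 10 window. For a visit on Day 183 the window becomes Days 155 to 183, which is 183 − 155 + 1 = 29 days.

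A cap at last dose + 25 days would be weaker. It would remove Days 202 to 211 but leave 201 − 183 = 18 days after the visit.

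The cost is one programming rule using visit dates already on the eCRF, with no new data and no change to any tested endpoint. The downside is that a subject whose only qualifying days fall after the visit becomes missing at Week 26 for Tables 2.401 and 2.403. Probably few subjects are affected.

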
 To compare the effects between the 2 treatment groups on patient-reported outcomes to diabetes medication and to further assess glycemic parameter, weight, and composite endpoints 	
 Patient-reported outcomes to diabetes medication at Baseline/Randomization, Week 10, and Week 26: 
 Treatment-related impact measure for diabetes (TRIM-Diabetes) questionnaire Hypoglycemia fear survey-II (HFS-II) worry subscale Additional glycemic parameter, weight, and composite endpoints: 
 HbA_{1c} change from Baseline at Week 26 by baseline FPG tertiles FPG change from Baseline at Week 26 by baseline FPG tertiles 24-hour glucose profile: 8-point self-monitored blood glucose (SMBG) profile at Baseline/Randomization, Week 10, and Week 26 (before and 120 minutes after the 3 main meals, at bedtime, and at 2 AM) Mean daily blood glucose based on the 8-point SMBG profile at Baseline/Randomization, Week 10, and Week 26 Number (and percentage) of subjects with ≤ 1 kg weight gain at Week 26 Percentage of subjects achieving HbA_{1c} $< 7.0\%$ without weight gain and without hypoglycemia with blood glucose < 56 mg/dL (< 3.1 mmol/L) regardless of symptoms at Week 26 Proportion of subjects treated with once-weekly albiglutide that are able to totally replace or decrease prandial insulin without worsening HbA_{1c} control (worsening defined as $> 0.3\%$ increase in HbA_{1c} compared with baseline HbA_{1c}) at Week 26

 Analysis of genetic sampling may also be performed 	
 Genetic sampling

 Analysis of novel biomarkers may also be performed 	
 Novel biomarker analysis may be performed; a decision on whether to analyze novel biomarker samples may be made after review of efficacy and safety

Objective	Endpoint
	endpoints at the end of the study or other emerging information that may become available during the study

[figure not shown]

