	
baseline FPG tertiles
 
 • 24-hour glucose profile: 8-point self-monitored blood glucose (SMBG) profile at Baseline/Randomization, Week 10, and Week 26 (before and 120 minutes after the 3 main meals, at bedtime, and at 2 AM) • Mean daily blood glucose based on the 8-point SMBG profile at Baseline/Randomization, Week 10, and Week 26 • Number (and percentage) of subjects with ≤ 1 kg weight gain at Week 26 • Percentage of subjects achieving HbA_{1c} $< 7.0\%$ without weight gain and without hypoglycemia with blood glucose < 56 mg/dL (< 3.1 mmol/L) regardless of symptoms at Week 26 • Proportion of subjects treated with once-weekly albiglutide that are able to totally replace or decrease prandial insulin without worsening HbA_{1c} control (worsening defined as $> 0.3\%$ increase in HbA_{1c} compared with baseline HbA_{1c}) at Week 26

 • Analysis of genetic sampling may also be performed 	
 • Genetic sampling

 • Analysis of novel biomarkers may also be performed 	
 • Novel biomarker analysis may be performed; a decision on whether to analyze novel biomarker samples may be made after review of efficacy and safety endpoints at the end of the study or other emerging information that may become available during the study

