8.1.2. Key Secondary Efficacy Endpoints

8.1.2.1. Proportion of Subjects Who Do Not Meet Prespecified Criteria for Severe, Persistent Hyperglycemia through Week 26

For this key secondary endpoint, subjects who do not meet prespecified criteria for severe, persistent hyperglycemia through Week 26 will be defined operationally as those subjects treated with once-weekly albiglutide that are able to replace prandial insulin without lispro re-introduction through Week 26. Note: For lispro re-introduction through Week 26 the time window is defined up to Week 25.

Proportion of subjects that are able to discontinue insulin lispro at Week 4 and do not meet prespecified criteria for severe, persistent hyperglycemia through Week 26 will be summarized descriptively for all the Albiglutide + Insulin Glargine arm subjects and for

subgroups of baseline HbA_{1c} category (<8.0%, ≥8.0%), region, (<65 years versus ≥65 years), current use of metformin (Yes, No) in the FA population. The 95% confidence interval of the proportions of subjects will be provided.

The insulin lispro that was re-introduced to albiglutide subjects will be characterized. Summary statistics for the number of injections, total dose, and time-to-re-introduction will be presented.

Additional exploratory analyses to identify potential risk factors for lispro re-introduction will be investigated. Potential risk factors include: baseline HbA_{1c}, baseline HbA_{1c} category, age, age category, metformin-use, duration of diabetes, weight, BMI, BMI category, time in insulin (at baseline), baseline HbA_{1c}, and total insulin dose at baseline. Time in insulin (at baseline) is defined as the earliest start date of prior insulin medications taken minus the date of first date of randomized study medication, plus 1.

8.1.2.2. Percentages of Subjects with Severe or Documented Symptomatic Hypoglycemia through Week 26

The percentage of subjects with severe or documented symptomatic hypoglycemia will be summarized descriptively by treatment and analyzed using a Cochran-Mantel-Haenszel (CMH) test, stratified by baseline HbA_{1c} category, region, age category (<65 years versus ≥65 years), current use of metformin (Yes, No) in the FA population.

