Other Exploratory Endpoints					
2.201	FA		Summary Statistics for TRIM-Diabetes Questionnaire Total and Individual Domain Scores by Visit		
2.202	FA		Analysis of Change from Baseline in TRIM-Diabetes Questionnaire Total Score over Time		
2.203	FA		Analysis of Change from Baseline in TRIM-Diabetes Questionnaire Treatment Burden Score Over Time		
2.204	FA		Analysis of Change from Baseline in TRIM-Diabetes Questionnaire Daily Life Score over Time		
2.205	FA		Analysis of Change from Baseline in TRIM-Diabetes Questionnaire Diabetes Management Score over Time		
2.206	FA		Analysis of Change from Baseline in TRIM-Diabetes Questionnaire Compliance Score over Time		
2.207	FA		Analysis of Change from Baseline in TRIM-Diabetes Questionnaire Psychological Health Score over Time		
2.301	FA		Summary Statistics for HFS-II Questionnaire Worry Subscale Total Score by Visit		
2.302	FA		Analysis of Change from Baseline in HFS-II Questionnaire Worry Subscale Total Score over Time		

Efficacy: Tables					
No.	Population	IDSL / TST ID / Example Shell	Title	Programming Notes	Deliverable [Priority]
2.401	FA		Summary Statistics for 8-Point Self-Monitored Blood Glucose (mmol/L) Profile by Visit		
2.402	FA		Summary Statistics for Daily Average Glucose Concentration from 8-Point Self-Monitored Blood Glucose (mmol/L) Profile by Visit		
2.403	FA		Analysis of Change from Baseline in Daily Average Glucose Concentration from 8-Point Self-Monitored Blood Glucose Concentration (mmol/L) Over Time		
2.501	FA		Analysis of Proportion of Subjects with <= 1 Kg Weight Gain at Week 26		
2.601	FA		Analysis of Proportion of Subjects Achieving HbA1c < 7.0% without Weight Gain and Without Hypoglycemia with Plasma Glucose <3.1 mmol/L (<56 mg/dL) Regardless of Symptoms at Week 26		
2.701	FA		Proportion of Subjects Treated with Once-weekly Albiglutide That Are Able to Totally Replace Prandial Insulin without Re-introduction of Inuslin Lispro and without Worsening HbA1c Control at Week 26		

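### The exploratory endpoint allows prandial insulin to be replaced or decreased, but SAP 8.2.9 has no rule for a decrease and its only table, 2.701, covers total replacement alone

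*SAP*

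**What the plan says.** The endpoint is stated the same way in the Protocol Summary, Protocol Section 2, SAP 2.2 and SAP Table 5. In Protocol Section 2 it is the proportion of albiglutide subjects "able to totally replace or decrease prandial insulin without worsening" HbA1c control, where worsening means a rise of more than 0.3% from baseline at Week 26.

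The analysis text and the display differ from this:

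- The heading of SAP 8.2.9 contains "Able to Totally Decrease Prandial Insulin without Worsening". The section repeats the 0.3% threshold and adds only: "This exploratory endpoint will be analyzed in the same manner as specified in Section 8.1.2.1".
- SAP 8.1.2.1 deals with a key secondary endpoint. It defines success operationally as being "able to replace prandial insulin without lispro re-introduction through Week 26", with the re-introduction window ending at Week 25. The proportion "will be summarized descriptively for all the Albiglutide + Insulin Glargine arm subjects" in the FA population, and by subgroup, with a 95% confidence interval.
- The only table planned for the exploratory endpoint, Table 2.701 in SAP 11.14.4, is titled for subjects "That Are Able to Totally Replace Prandial Insulin without Re-introduction of Inuslin Lispro and without Worsening HbA1c Control at Week 26".
- SAP 2.1, which sets out changes from the protocol's analysis, lists only the switch from insulin dose taken to insulin dose prescribed.

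**The concern.** The option to decrease is what separates this endpoint from the key secondary endpoint on replacement without re-introduction. Without it, Table 2.701 is the key secondary result with an HbA1c condition added.

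Subjects on reduced lispro are a group that the design creates. Under Protocol 5.1.3.5, lispro can return stepwise after Week 8, and these subjects stay in the study on albiglutide plus lispro. SAP 8.1.2.4 expects them to take one, two or three lispro injections a day. If the table is produced as titled, the report will not say how many subjects lowered their prandial insulin without losing control. A reader could also take a stricter proportion for the one that the protocol defined.

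**Working it through.** The plan states no figure for this endpoint, so the check is a comparison of texts and a statement of direction.

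**Step 1: the definitions side by side.**

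| Place | Replace | Decrease | HbA1c condition |
|---|---|---|---|
| Protocol Summary and Section 2 | yes | yes | yes |
| SAP 2.2 and Table 5 | yes | yes | yes |
| SAP 8.2.9 heading | dropped | yes | yes |
| SAP 8.2.9 text | no rule | no rule | yes |
| SAP 8.1.2.1 (referred to) | yes, as no re-introduction | no | no |
| SAP Table 2.701 | yes, as no re-introduction | no | yes |

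No section says what lispro dose counts as a decrease, or against which reference.

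**Step 2: does another display recover it?** Table 2.32 gives characteristics by re-introduction status, Table 2.33 the daily lispro dose in re-introduced subjects, Table 2.34 injections per day, and Tables 2.65 and 2.66 the bolus dose analyses. As titled, none classifies a subject's dose as below a reference dose and joins that to the same subject's HbA1c change.

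**Step 3: direction.** Let N be the albiglutide arm in the FA population. Let A be the subjects with no re-introduction and no worsening. Let B be the subjects with lispro re-introduced, a reduced dose and no worsening.

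- Protocol-defined proportion = (A + B)/N
- Table 2.701 as titled = A/N
- Difference = B/N, which is zero or positive

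This holds if both proportions use the same N and treat missing Week 26 HbA1c in the same way.

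**Step 4: scale.** With about 397 subjects planned in the arm, each subject in B lowers the reported proportion by 1/397 = 0.25 percentage points. The documents give neither a re-introduction rate nor doses after re-introduction, so B is unknown. Purely as assumptions, B of 5%, 10% or 20% of the arm (about 20, 40 or 79 subjects) would mean gaps of 5, 10 or 20 points. These restate the assumption and are not estimates.

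**Step 5: the reference dose.** Protocol Table 2 halves each lispro dose at Baseline/Randomization in this arm. If D is the daily dose at the end of Standardization, the dose prescribed at the Baseline visit could be D or D/2. A Week 25 dose between D/2 and D is a decrease against the first and not against the second. The word baseline alone therefore does not settle who succeeds.

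**The case against.** The strongest objection is that the cross-reference may borrow only a method. SAP 8.2.7 and 8.2.8 are sent to 8.1.2.2 with almost the same phrase, and they clearly take over its tests and not its hypoglycemia endpoint. The no-re-introduction rule in 8.1.2.1 is also introduced as applying to that key secondary endpoint. This stands: 8.2.9 alone does not prove that the endpoint is analysed as replacement only. Its heading keeps the decrease and loses the replacement, which looks like dropped words. On this reading, however, 8.2.9 has no success rule at all, and the title of Table 2.701 still excludes subjects who only decreased. The point rests mainly on that title.

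A second objection is that reduced lispro use is reported elsewhere. That is partly right. SAP 6.7 and 8.1.2.1 characterise re-introduced lispro, and Listings 145 and 150 carry HbA1c and insulin surveillance data. A reader might infer that the information is lost. It is not: what is missing is one joint proportion, which could be derived from data already listed.

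A reader might also infer a deliberate narrowing of the endpoint. SAP 2.2 and Table 5 restate it unchanged, so the documents support an inconsistency within the SAP and not a decision.

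**Conclusion.** The mismatch is real and minor. Four statements of the endpoint allow a decrease, the analysis section does not define one, the only table omits it, and SAP 2.1 does not declare the narrowing. Followed as titled, Table 2.701 gives a proportion equal to or below the protocol-defined one.

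Two stronger readings go too far. One is a stated shortfall of so many percentage points, for which the documents give no basis. The other is that the SAP labels subjects who decreased as failures. It does not use that term. Their exclusion from the numerator follows from the Table 2.701 title, and their place in the denominator follows only if the whole-arm denominator of 8.1.2.1 is carried over.

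The endpoint is exploratory and defined for the albiglutide arm alone, and it lies outside the testing sequence in SAP 11.10. Alpha, power and the primary conclusion are not affected.

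**What to change.** Restore both routes, replaced or decreased, in the heading and text of SAP 8.2.9 and in the title of Table 2.701. Then add to 8.2.9:

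- **Totally replaced:** no lispro re-introduction through Week 25, as in 8.1.2.1, with a Week 26 HbA1c change of at most 0.3%.
- **Decreased:** lispro re-introduced, with the prescribed total daily lispro dose at Week 25 below the prescribed dose at the end of Standardization, before the halving at randomization, and a Week 26 HbA1c change of at most 0.3%. This is a classification for analysis only. State that any reduction counts, since neither document sets a minimum.
- **Missing data:** state how a missing Week 26 HbA1c or Week 25 dose is handled. SAP 8.1.3.3 already has a rule for missing HbA1c in the target-response proportions that could be reused.

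Show the two components as separate rows with their total. If replacement only is what is wanted, list the narrowing and its rationale in SAP 2.1 and align SAP 2.2 and Table 5.

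The cost is SAP wording, one derived variable and extra rows in one table. No new data are needed: SAP 6.8 records prescribed lispro on the Insulin Surveillance eCRF page from Week -4, and SAP 8.1.2.4 already takes the Week 25 prescription as the Week 26 dose in this arm.
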